Study Title:

The Accuracy of Smartphone Pulse Oximetry in Patients Visiting an Outpatient Pulmonary Function Lab for a 6-Minute Walk Test

Primary Investigator:

[name], RRT-ACCS, AE-C, FAARC, FCCP
Director of Clinical Education
Assistant Professor
Rush University, Department of Respiratory Care

Co-Investigator:

[name]
M.S. in Respiratory Care | Class of 2018
Department of Respiratory Care
Rush University Medical Center

[name], MS, RRT, RPFT
Pulmonary Function Lab
Rush University Medical Center

October 13, 2019

Aim of the Study

The primary aim of this research is to determine the accuracy of smartphone pulse oximeters in detecting blood oxygen saturations, episodes of desaturations, and heart rate by comparing results to a Masimo[©] hospital-grade pulse oximeter.

Introduction

Digital innovations have made it possible for consumers to use mobile devices for medical purposes. They can be used to monitor physiological parameters such as blood pressure, heart rate, blood oxygen saturation, and body temperature. They can also be used to conduct diagnostic tests, request prescription refills, and relay medical information to physicians.¹ Consequently, the healthcare sector is being profoundly affected by this emerging technology.^{1,2} A frequent reliance on mobile devices has been reported among healthcare practitioners (HCPs) and students, with 85% reporting the use of a mobile device at least once daily for clinical purposes. The most common use was for information, time management, or communication relating to education and patient care.³ In 2010, approximately 50 percent of physicians used a mobile phone or a smart mobile device as a part of his or her practice. In 2015, that number increased to approximately 70 percent. The overall growth of applications (apps) was 38.1 percent, compounded annually over the past five years; in regards to medical apps, the growth was documented at 41.9 percent.⁴

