Alexander et al compared four different smartphone application-based monitors: Instant Blood Pressure, Instant Blood Pressure Pro, Pulse Oximeter, and Pulse Oximeter Pro. Three different parameters were measured using these four devices: heart rate, blood pressure, and SpO₂. The comparison revealed a large degree of variance in the values between the Instant Blood Pressure, the Instant Blood Pressure Pro, the Pulse Oximeter, and the Pulse Oximeter Pro.⁹ Another study by Petersen and Dumont was conducted that compared the response of motion artifact of three different mobile pulse oximeter devices, all interfaced to Apple iPod Touch devices: the Nonin Xpod, the Masimo OEM inline module, and an Audio Phone Oximeter prototype. The study showed that there was more motion artifact at lower saturations for all three of the devices. The most valid measurements was found with Masimo's mobile device at readable values of approximately 85 to 87 percent.¹⁰

While the technology to detect SpO₂ and heartrates on smartphones is emerging and widely available, there is no evidence supporting its use in patients with lung disease. Smartphone pulse oximetry could be useful in individuals with acute or chronic lung disease; however, device inaccuracies could be harmful if desaturations are not detected immediately. It is not known how accurately these devices detect oxygen saturation/desaturation in patients with acute or chronic lung conditions. This study will be used to evaluate the accuracy of smartphone pulse oximeters in patients that will be undergoing a six-minute walk test in a pulmonary function lab.

Experimental Design and Methods

This is a prospective, observational study conducted at the pulmonary function laboratory at Rush University Medical Center. Subjects (n=48) will be selected if they are of 18 years of age or older, ambulatory, scheduled for a six-minute walk test, and agree to participate. The following information will be collected:

- First name
- Last name
- Date of Birth
- Age
- Height
- Gender
- Race/Ethnicity
- Oxygen use and frequency (if they are already on oxygen)
- Pulmonary Disorders
- Borg's Dyspnea Scale
- Heart rate (hospital-grade pulse oximeter and external and built-in smartphone pulse oximeter; pre- and post- test)
- SpO₂ (hospital-grade pulse oximeter and external and built-in smartphone pulse oximeter; pre- and post- test)

Procedures

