For every patient that meets inclusion criteria, demographic information such as: age, race, and gender will be collected. Weight will be measured in the pulmonary function clinic by the designated respiratory therapist. Heart rate and SpO₂ measurements will be taken per normal routine during the six-minute walk test (before and after the test). Parameters will be measured

using an iPhone attached external pulse oximeter (Kenek Edge, LionsGate Technologies, Vancouver, Canada), a Samsung S8 (Samsung Electronics Co. Inc., Seoul, South Korea) built-in pulse oximeter, and a Masimo[®] (Masimo Corporation, Irvine, California) hospital-grade pulse oximeter. Readings will be obtained before and after the test. All three devices will be used to obtain readings from a single arm, consecutively. Each reading will be recorded manually by persons involved in the research. Each reading will be recorded using RedCap software and later transferred to SPSS software for data analysis. All data placed on the RedCap software and SPSS will only be accessible by the primary investigators.

Subject Population

Inclusion criteria

Ambulatory patients, 18 years and older, visiting the pulmonary function laboratory at Rush University Medical Center for a 6-minute walk test (n = 30) that agree to participate.

Exclusion criteria

Patients who are under the age of 18 years or patients with high blood pressure above 180/90 mm Hg or pressure below 70/50 mm Hg will be excluded. Patients who are dizzy, light-headed or have severe headaches, if SpO₂ at or below 85% on supplemental oxygen or if patients are on oxygen greater than 4 liters per minute will be excluded. Gait issues that may result in a fall or patient walks with a walker and did not bring the device to this visit will be excluded.

Consent and Recruitment Procedure

Recruitment will be based on inclusion and exclusion criterion. Study subjects will be recruited through convenience sampling of patients attending the pulmonary function lab for a 6-minute walk test at Rush University Medical Center. Verbal consent will be obtained during the time of subject interaction. Waiver of written consent will be requested since no invasive procedures are involved or procedures that would potentially be harmful to the participants.

Compensation

There is no compensation provided in this study. The participant is not required any other follow up after obtaining this initial data.

Special Precautions

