There are no special precautions needed in this study. Standard disinfection policies apply. Personal protective equipment and standard protocol should be followed at all times. Patient safety and privacy will be addressed at all times.

Confidentiality

Persons who are primary investigators and secondary investigators, along with the IRB, will have access to patient records. To protect patient privacy and confidentiality, each patient will be assigned a subject identification number. Names will not be included in the data analysis. The investigators will strictly adhere to HIPAA and IRB guidelines to ensure that patient confidentiality is maintained.

Plans for Data Analysis

Data for each subject will be recorded in RedCap which will only be accessed by study investigators. Means and standard deviation will be calculated for age, gender, race, heart rate,

and pulse oximeter reading from hospital-grade and smartphone pulse oximeters. A t-test will be used to determine any significant association between age, gender, diagnosis, weight, and oxygen use ($p < .05$). Alpha will be used as 0.05 and beta will be used as 0.20. It can be predicted that these tests will be parametric. A scatter plot will be used to assess bias and validity.

Independent variables: Type of pulse oximeter

Dependent variables: SpO₂ and heart rate

Co-variables: body mass index, admitting diagnosis, age, site of measurement, oxygenation status, skin pigmentation, nail color, and pulmonary disorders.

References

1. Topol E. How technology is transforming healthcare. 2013;2017(08/02). Web.
2. Huston C. The impact of emerging technology on nursing care: warp speed ahead. *Online J Issues Nurs* 2013;18(2):1.
3. Ventola CL. Mobile Devices and Apps for Health Care Professionals: Uses and Benefits. *P T* 2014;39(5):356-364.
4. Heath S. mHealth App Market Sees \$400 Million Growth in Five Years. 2015;2017(08/03). Web.

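### The primary aim is accuracy against the Masimo, but no planned statistic measures phone-minus-Masimo error in individual patients, and desaturation is neither defined nor analysed

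*Combined protocol and SAP*

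**What the plan says.** - **Aim of the Study.** The primary aim is to "determine the accuracy of smartphone pulse oximeters in detecting blood oxygen saturations, episodes of desaturations, and heart rate", by comparison with the Masimo.
- **Introduction.** The rationale warns that "device inaccuracies could be harmful if desaturations are not detected immediately".
- **Procedures and Appendix.** "Readings will be obtained before and after the test". The three devices are used one after another on the same arm. The form has a Masimo, a Kenek/Apple and a Samsung column at pre-test and at post-test.
- **Plans for Data Analysis.** Means and SDs are planned for several variables, including heart rate "and pulse oximeter reading from hospital-grade and smartphone pulse oximeters". The only test is described as follows: "A t-test will be used to determine any significant association between age, gender, diagnosis, weight, and oxygen use". Then: "A scatter plot will be used to assess bias and validity". The variables are declared as "Independent variables: Type of pulse oximeter" and "Dependent variables: SpO₂ and heart rate".

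The plan contains no paired difference, SD of differences, limits of agreement, root-mean-square error, agreement coefficient or acceptable error. Desaturation is not among the dependent variables. The only SpO₂ threshold, 85%, is an exclusion criterion for patients on supplemental oxygen.

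**The concern.** Accuracy against a reference is a property of the paired readings: how far this phone is from the Masimo in this patient. Means and SDs per device discard the pairing. A phone that follows the Masimo closely and one that does not can produce the same summary table. Only the plot could tell them apart, and nothing fixed in advance says what would be plotted, what would be calculated from it, or how large an error would be too large.

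If the declared variables are meant to imply a t-test between devices, that test addresses mean bias only. For a given bias, a noisier phone is more likely to give a non-significant result, which is easily misread as agreement.

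Desaturation is one of the three targets in the primary aim, and the one the Introduction ties to possible harm. As written it yields no result.

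**Working it through.** **The plan's own figures.** There is no agreement figure to reproduce. Alpha 0.05 and beta 0.20 are stated without an effect size, SD or margin, so neither stated sample size can be derived (48 under Experimental Design and Methods, 30 under Inclusion criteria). Both are used below. SDs, correlations, bias and desaturation rates are not in the documents; they are assumptions, shown as ranges.

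**1. What device means and SDs leave open.** With equal SD *s* on both devices and between-device correlation *r*, SD of differences = s√(2(1−r)), and the 95% limits of agreement are bias ± 1.96 times that. The SD formula needs no normality. Example: s = 3, r = 0.95 gives 3√0.10 = 0.949, and 1.96 × 0.949 = 1.86.

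| Measure, assumed SD | r = 0.95 | r = 0.8 | r = 0.5 |
|---|---|---|---|
| SpO₂, 2 points | ±1.24 | ±2.48 | ±3.92 |
| SpO₂, 3 points | ±1.86 | ±3.72 | ±5.88 |
| SpO₂, 4 points | ±2.48 | ±4.96 | ±7.84 |
| Heart rate, 10 bpm | ±6.2 | ±12.4 | ±19.6 |
| Heart rate, 15 bpm | ±9.3 | ±18.6 | ±29.4 |
| Heart rate, 20 bpm | ±12.4 | ±24.8 | ±39.2 |

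Every entry in a row comes from the same device means and SDs. SpO₂ readings are skewed, whole numbers and capped at 100, so the SD 3 row was also simulated as 100 minus a gamma variable (mean 6, SD 3), correlated through a Gaussian copula and rounded, with 2,000,000 pairs. Device means stayed at 94.0 and SDs at 3.01, while 1.96 × SD of differences was 2.1, 3.9 and 6.0.

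**2. A device t-test, if one is intended.** Paired t-test, two-sided 0.05, true bias 1 point, s = 3, noncentral t:

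| n | r = 0.95 | r = 0.8 | r = 0.5 |
|---|---|---|---|
| 48 | >99.9% | 95% | 62% |
| 30 | >99.9% | 80% | 42% |

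The same bias is missed more often as the phone gets noisier. With zero bias the test rejects about 5% of the time at every correlation, so it says nothing about scatter.

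**3. Desaturation.** Suppose a proportion *p* of readings falls below the cut-off on each device and readings are bivariate normal. Sensitivity = P(both below)/p.

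| p | r = 0.95 | r = 0.5 |
|---|---|---|
| 10% | 78% | 32% |
| 20% | 82% | 44% |
| 30% | 85% | 52% |

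Equal *p* means no bias. Bias matters as well: with s = 3, r = 0.95 and 20% below on the Masimo, a phone reading 1 point high has sensitivity 57%, and one reading 1 point low 96%.

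**4. What a repaired analysis could deliver.**

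- CI half-width of each limit = t(0.975, n−1) × √(1/n + 1.96²/(2(n−1))) SDs of differences: 0.50 at n = 48 and 0.65 at n = 30.
- If 20% of patients desaturate (about 10 of 48, or 6 of 30) and all are detected, the exact lower 95% bound for sensitivity is 0.025^(1/10) = 69% or 0.025^(1/6) = 54%.
- Real change between consecutive readings widens the limits. With an assumed SD of 1 or 2 points, independent of device error, limits of ±1.86 become 1.96√(0.949² + 1²) = ±2.70 or 1.96√(0.949² + 2²) = ±4.34.

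**The case against.** The best defence is that the plan is terse rather than wrong. Device type is declared as the independent variable, the plot is given an agreement task, and a plot meant to assess bias could be a difference plot with a bias line and limits. The device means already give a crude bias by subtraction. Nothing is lost for good, because the paired readings are collected and the estimates can be computed later. The device t-test criticised above is not written in the plan, and every magnitude rests on assumed values.

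Much of this is fair. The plot may have been meant as a difference plot, the t-test argument is conditional, and the figures are illustrations rather than bounds. The sensitivity contrast by correlation alone also leaves out the part played by bias, some of which the device means would reveal.

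The defence does not fill the gap. A difference of means is average bias and cannot be turned into individual error without the correlation. An unspecified plot fixes no number and no criterion before the data are seen. Nothing in the documents can be read as a definition or analysis of desaturation; the 85% value decides who may enter the study.

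**Conclusion.** The concern holds and should be fixed before analysis. Followed as written, the plan gives no measure of individual error for SpO₂ or heart rate and no result at all for desaturation, so its primary question is not quantified.

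Under the assumptions above (equal means, SD 3), one summary table is compatible with SpO₂ limits about three times wider in one case than in another (5.88/1.86 ≈ 3.2). That ratio depends only on the two correlations, 0.95 and 0.5, and not on the SD. The actual SDs and correlations are unknown. That device means and SDs do not determine individual error is true whatever their values.

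**What to change.** Essential changes to Plans for Data Analysis:

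- For each phone, for SpO₂ and heart rate, at pre-test and post-test separately, analyse the paired phone-minus-Masimo difference. Report mean bias with 95% CI, the SD of differences, and 95% limits of agreement with CIs. Root-mean-square error is a useful single summary.
- Specify the plot as difference against mean, with bias and limits drawn.
- Have the investigators state, before analysis, the acceptable error against which the limits and their CIs will be read. A pass/fail rule is not required.
- Have the investigators define desaturation on the Masimo reading. Report each phone's sensitivity and specificity with exact 95% CIs. Otherwise remove desaturation from the primary aim.

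Supporting changes:

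- There are 2 phones × 2 measures × 2 times = 8 comparisons. Post-test SpO₂ for each phone is a reasonable lead, with the rest supporting. It is also the comparison most exposed to real change between consecutive readings, so the investigators should confirm the choice and give their reason.
- Count missing and failed readings per device, with a code for failures, because the form has no field for them.
- Reconcile the two sample sizes.

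The cost is about a paragraph of wording and a little more analysis, using readings already on the form. Wording cannot recover everything, and the plan should say so. Readings before and after the walk cannot capture episodes during it. Change between consecutive readings will widen the limits, and any average change will appear as bias. Precision will be modest at either sample size.

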Appendix

Subject ID _____

Gender Male Female Transgendered

Ethnicity White/Caucasian
 Hispanic/Latino
 Black/African American
 Asian
 Other (specify) _____

Age _____

Weight (lbs) _____

Diagnosis Asthma
 Congestive obstructive pulmonary disorder (COPD)
 Cystic Fibrosis
 Pulmonary Fibrosis
 Chronic Bronchitis
 Bronchiectasis
 Congestive Heart Failure
 Stroke
 Heart Attack/Failure
 Pulmonary Hypertension
 Cancer
 Renal Disease
 Other (specify) _____

Oxygen use? Yes No

If yes, indicate the amount of oxygen used

○ ○ ○ ○ ○
< 2L/min flow 2-6 L/min flow 6-10 L/min flow As needed Only after physical activity

	Pre-test Vital Signs			Post-test Vital Signs		
	Masimo	Kenek/Apple	Samsung	Masimo	Kenek/Apple	Samsung
Heart Rate						
SpO ₂						
Blood Pressure						
RR						
Borg Dyspnea Scale
